1.0 Objectives

1.1 Primary Objectives

- To determine the safety of porfimer sodium (Photofrin®) mediated interstitial photodynamic therapy (I-PDT) in patients with locally advanced or recurrent head and neck cancer (HNC).
 - o To determine the recommended light irradiance dose for a future Phase 2 trial of Photofrin® mediated I-PDT in patients with locally advanced or recurrent HNC.

1.2 Exploratory Objectives

• To assess the objective tumor response rate.

2.0 Background

2.1 Locally Advanced Head and Neck Cancer and Current Treatment Approaches

Recent cancer statistics in the U.S. predicted that 51,540 men and women would be diagnosed with and 10,030 men and women would die of cancer of the oral cavity and pharynx in 2018.(1) These numbers represent an estimate increase of 21% and 19% in incidence and death rate, respectively, when compared to the published statistics in 2014 (i.e., 42,440 and 8,390 incidence and death rate, respectively).(2) These data (and statistics for 2015-2017, (3-5)) suggest that there is a constant increase in incidence and death rates for patients with HNC in the U.S. Although approximately 60–65% of these patients can be cured with surgery, chemoradiation, and targeted therapy, the rest will eventually die of local regional recurrent and/or metastatic disease. Among them, more than 40-60% of the patients will have persistent or recurrent local regional disease.(6) Locally advanced and recurrent head and neck squamous cell carcinoma (HNSCC) are frequently resistant (refractory) to standard chemotherapy and are typically not amenable to receive curative radiation therapy.(7-10) The newest immunotherapy regimens result in encouraging but limited overall response rate of no more than 16%.(11, 12) These aggressive tumors grow to destroy vital structures and patients often die from airway obstruction and uncontrolled local hemorrhage.(13)

Quality of life and survival of these patients are severely compromised due to local effects of recurrent disease. Systemic chemotherapy is a widely used tool for reducing tumor burden, with the assumption that this leads to alleviation of tumor-related symptoms and prolongs survival. Platinum agent (cisplatin or carboplatin) and 5-FU have been considered the most effective first line chemotherapy for these patients. A phase III study (EXTREME study) has shown that the addition of Cetuximab can improve the response to 36% and the median survival from 7 to 10.3 months, in comparison to a regimen that includes only platinum and 5-FU.(10) This SoC therapy, however, is associated with extensive morbidity that relates to the use of the platinum agent and 5-FU, particularly. The potential adverse events include bone marrow suppression, neuropathy, ototoxicity, renal toxicity, mucositis, gastrointestinal and hematologic toxicities.(10) Furthermore, poor tolerability of the aforementioned chemotherapy regimen limits this approach to a relatively small number of patients that can receive this therapy.

Salvage surgery has limited success that is associated with sever disfigurement and morbidity (13). Re-irradiation (Re-RT) with concurrent chemotherapy (Re-CTRT) has been suggested for selected patients with locally advanced, locoregional recurrent HNC in a previously irradiated field.(7)

Several groups have reported their retrospective experiences with Re-RT, and have suggested a feasibility and survival benefit of this approach.(14, 15) A phase III multi-institutional study conducted in France evaluated the efficacy of Re-CTRT after salvage surgery and demonstrated that deaths due to locoregional recurrence were less frequent in the Re-CTRT arm than in the wait and see (WS) arm.(16) However, treatment related deaths were more frequent in the Re-CTRT arm than in the WS arm.(16) Patients with severe toxicity, such as osteonecrosis and trismus from prior radiation have typically been excluded from reported experiences with Re-RT.(17) Therefore, Re-RT is still considered experimental by many, and feasible only in a limited patient population.(17, 18)

2.2 Clinical Use of Porfimer Sodium (Photofrin®)

The U.S. Food and Drug Administration (FDA) approved the use of porfimer sodium mediated PDT for the treatment of esophageal cancer, NSCLC and High-Grade Dysplasia in Barrett's Esophagus.(19, 20) In PDT, systemic administration of porfimer sodium is followed by illumination of the target tissue with visible light that leads to the generation of reactive oxygen species, notably singlet oxygen.(21) Porfimer sodium is being used off label and in clinical studies to treat many other cancers, including HNC.(22-27) These were retrospective studies in patients with early stage (T1, T2) HNSCC. Theses researchers reported complete response rates of 80-85%, suggesting that porfimer sodium mediated PDT can be effective in treating HNSCC.

A detailed description of the specific indications and, discussion of the clinical pharmacology, pharmacokinetics, and toxicology of porfimer sodium can be found in the Photofrin® prescribing information (http://www.photofrin.com/wp-content/uploads/2013/02/prescribing-info.pdf).

2.3 Clinical Use of PDT with Chemotherapy

PDT with photosensitizers (PSs) in combination with chemotherapy has shown promising outcomes in down staging and improve local control, overall all survival and quality of life of patients with advanced non-small cell lung cancer (NSCLC).(28-30) The PDT was done pre or intraoperatively and in one study chemotherapy was administered on day of or day after PDT in patients with stage IIa to IV NSCLC.(28) (30)

Several retrospective studies suggested that Photofrin® mediated PDT with chemotherapy could improve the outcomes for patients with advanced esophageal cancer, and for patients with unresectable cholangiocarcinoma.(31-33) Photofrin® mediated PDT + chemotherapy has been reported to be better than either PDT alone or chemotherapy alone in the treatment of unresectable cholangiocarcinoma and advanced esophageal cancer in a limited number of studies.(31, 33, 34) A relatively large retrospective study by Lindenmann et al. (35) suggested that adding Photofrin® mediated PDT prior to standard of care (n=118) resulted in better overall survival than adding PDT after SoC (n=130) in patients with inoperable esophageal cancer. (35) That report was in agreement with Li et al. 2010(31) who found that Photofrin® mediated PDT before chemotherapy (n=33) is associated with significantly better overall response when compared with either Photofrin® mediated PDT (n=27) or chemotherapy alone (n=30) in patients with advanced esophageal cancer.(31)

Importantly, the above-mentioned studies did not report of added toxicity or serious adverse events due to the combination of PDT and chemotherapy.

Our preliminary experience suggests that porfimer sodium mediated I-PDT with chemotherapy is safe and may hold promise for patients with locally advanced recurrent HNSCC.(36)

2.4 Preclinical Studies in Photofrin® Mediated I-PDT

Ongoing NCI funded preclinical studies at [name] laboratory ([name] PI, RO1CA193610-03) focus on defining the impact of intratumoral light fluence rate (i.e., could also be referred to as irradiance) on response and cure of locally advanced tumors revealed that:

- 1. Intratumoral light fluence rate appears to govern tumor response to I-PDT with Photofrin®.
- 2. The clinically approved light intensity (400 mW/cm) for Photofrin® can impede photoreaction. Lower light intensities can be used to administer a safe and effective I-PDT in mice bearing syngeneic locally advanced squamous cell carcinomas (SCCVII), which is appropriate for studying treatments for HNC. (37, 38)
- 3. Intratumoral 630 ± 3 nm laser light at a fluence rate of >8.6 mW/cm² and a fluence of >45 J/cm² delivered to 100% of the tumor volume will yield significantly (p<0.05, see **Figure** 1 below) high cure rate (70%-90%) in C3H mice bearing syngeneic 400-600 mm³ SCCVII tumors, a size of a locally advanced murine tumor. (39)
- 4. The finite element modeling (FEM) approach developed in [name] laboratory (40, 41), and will be use in this study, can be used to compute intratumoral fluence rate and fluence for a range of laser settings to guide Photofrin® I-PDT in C3H mice bearing locally advanced SCCVII tumors and guide safe and potentially effective treatment in New Zealand White rabbits bearing large VX2 tumors in the neck (Figure 2).

[figure not shown]

Figure 2. (A) Image of the rabbit treated with I-PDT. Visible in the image are the transparent close-end sharp catheters where treatment or dosimetry fibers were inserted. The blue probes are the optical thermometers that were placed on the tumor surface at margins. (B) 3-D representation of the treatment plan. The tumor is represented in blue. The intended treatment fibers are in green and the intended location of dosimetry fibers are in red. (C) 3-D representation of the intratumoral fluence rate throughout the tumor. (D) CT scan prior to treatment, and (E) a CT scan 41 days post treatment. (from [name] et al. Journal British of Cancer, (2018) 119, 1191-1199)

In previous publications we demonstrated that FEM could be used to plan and guide interstitial light delivery in models mimicking human tumors (40, 41). This modeling was used in a recent paper to guide I-PDT in the treatment of mice and NZW rabbits with VX2, part of the results are shown in figures 1 and 2 above. ([name] et al. Journal British of Cancer, Accepted for publication July 5, 2018).

We therefore propose to use the treatment planning to administer intratumoral 630 ± 3 nm laser light at >8.6 mW/cm2 and >45 J/cm2 to 100% of the tumor volume, as described in details in Section 10.2.

2.5 Study Rationale

There was a steady increase in incidence and disease related deaths for patients with HNC within the past 5 years in the US.(1-5) Patients die from locally advanced or recurrent HNC that have failed radiation therapy and have no viable treatment.(13, 42) Combination chemotherapy yields objective response rates of 10-36%.(8-10) Re-irradiation has been shown to be associated with significant toxicity.(16, 17, 42, 43) Salvage surgery is associated with prolonged hospitalization, and the cure rates are poor.(44, 45) These tumors are typically very heterogeneous, so theoretically their response to target therapy would be limited, and their response to immunotherapy (5-16%) is still being evaluated.(46)

Several review papers and reports of retrospective studies suggested that adding PDT or I-PDT to SoC targeted and chemotherapy can improve OS and QoL in patients with unresectable cholangiocarcinoma, advanced esophageal cancer, lung cancer, malignant mesothelioma, and pancreatic cancer. (31, 33, 34, 47-49) Non-randomized, single-site, studies of I-PDT with Temoporfin have shown promising results in the treatment of patients with locally advanced and

recurrent HNC that fail standard therapies.(50-52) However, I-PDT with Temoporfin is not approved for clinical use in the U.S. Photofrin® is the only clinically approved PS for treating cancerous tumors in the U.S.A. Our preliminary experience suggests that Photofrin® mediated I-PDT may hold promise for patients with locally advanced and recurrent HNC. (36) While I-PDT has the potential to provide local control, it is acknowledged that patients with locally advanced disease require systematic therapy. And multiples studies suggest that adding PDT to the SoC chemotherapy is safe (as summarized in the above section 2.3). We hypothesize that Photofrin® mediated I-PDT will be a safe treatment in patients with locally advanced or recurrent head and neck cancer that failed radiation therapy. The goal of this study is to test the safety and find the recommended light irradiance for porfimer sodium mediated I-PDT in patients with locally advanced or recurrent HNC who are not candidates for standard or salvage surgery or radiotherapy.

2.6 Correlative Studies

2.6.1 QUALITY OF LIFE EVALUATION

Several clinical studies suggested that PDT and I-PDT could improve QoL in patients with locally advanced HNC. (53-56) Few studies reported that I-PDT (with Temoporfin) reduced tumor related bleeding and pain, while improving breathing, speaking, swallowing, and appearance.(50, 51, 57) The impact of Photofrin® mediated I-PDT on QoL has not been evaluated, to date.

In this protocol, participants' QoL will be evaluated with an accepted University of Washington Quality of Life Questionnaire Version 4 (UW-QoLQ v4: see **Appendix E**) (58, 59). It has been tested in several prospective studies and found to be reproducible, reliable, and valid for HNC patients: it is simple to complete, employs a simple algorithm to compute the overall score, and is easy to interpret while yielding objective results.(60) This version includes 12 individual Likert-scale items and 4 global questions. Each participant's overall score on the UW-QoLQ v4 will be calculated at baseline, at 12-16 weeks, and at 30 days post final treatment.

2.6.2 IMMUNE STUDIES (OPTIONAL)

In order to determine whether I-PDT enhances anti-tumor immunity a multi-pronged analysis will be performed. The effect of I-PDT on T cell activity will initially be determined by examining the activation status of participant T cells before and after I-PDT administration. PDT induces a rapid pro-inflammatory response and such responses are associated with T cell activation and proliferation, which are frequently muted in participants with advanced cancer. Furthermore, the effects of I-PDT on patient anti-tumor T cells are unknown. T cell activation will be determined by flow cytometric analysis of peripheral blood T cells. Using T cell subtype and activation specific profiles, this analysis will allow us to determine whether administration of I-PDT alters both the activation status and ratio of T cell subtypes present before and after therapy.

The phenotypic characterization described above will determine whether I-PDT affects T cell activation and subtype ratio but will not discern whether the effects are tumor specific. Most tumors over-express p53 and many head and neck tumors overexpress HPV 16. Examination of changes in the immune response to p53 and/or HPV16 can reveal changes in tumor specific immune responses. To examine whether PDT enhances the immune response to p53 or HPV 16, peripheral blood T cells will be isolated and exposed to p53 and HPV 16 ex vivo. The ability of each participant's T cells to respond will be measured over time and compared against pre-treatment

APPROVED RPCI IRB 1/5/2024

Roswell Park Protocol No.: I 67918

results and to their ability to respond to antigens they have previously been exposed to, i.e., cytomegalovirus, Epstein-Barr virus and influenza virus (the so-called memory mix).

The third method for examining tumor specific T cells following I-PDT involves adding an additional marker to the flow panels described above. There is a well-defined p53 immune epitope that binds to the human major histocompatibility complex molecule HLAA2. Greater than 40% of the patients at Roswell Park express HLA-A2. HLA-A2 expression status of the trial participants will be determined. T cells isolated from HLA-A2+ participants will be tested for p53 reactivity using a flow cytometry reagent known as a tetramer that allows identification of p53 specific T cells.

Finally, we will examine changes in immune cell infiltrate and T cells activation status in tumors following PDT by comparing infiltrate and immune cell activation in tumors surgically removed from PDT treated patients to those removed non-PDT treated patients.

The mentioned immune studies analysis is optional for study participants with enough tissue for analysis as determined by the treating physician and dependent on amount of tumor, tumor location and if additional samples can be collected, which will vary based on the specifics of the tumor.

3.0 Inclusion and Exclusion Criteria

3.1 Inclusion Criteria

To be included in this study, participants must meet the following criteria:

- 1. Male or female patients age \geq 18 years of age.
- 2. Subjects must have an Eastern Cooperative Oncology Group (ECOG) performance status score of 0-2. Refer to **Appendix A.**
- 3. Patients with locally advanced or recurrent head and neck cancer who failed to respond to standard therapy and are not amenable to standard curative treatment.
- 4. Tumor accessible for unrestricted illumination for interstitial Photodynamic Therapy (PDT) (accessibility as determined by the physician).
- 5. Life expectancy of at least 6 months, in the judgment of the physician.
- 6. Subjects of child-bearing potential must agree to use adequate contraceptive methods (e.g., hormonal or barrier method of birth control; abstinence) prior to study entry and for the duration of study participation. Should a woman become pregnant or suspect she is pregnant while she or her partner is participating in this study, she should inform her treating physician immediately.
- 7. Subject must understand the investigational nature of this study and sign an Institutional Review Board approved written informed consent form prior to receiving any study related procedure.

Refer to Appendix B for the ELIGIBILITY VERIFICATION FORM: INCLUSION CRITERIA CHECKLIST.

3.2 Exclusion Criteria

Participants will be excluded from this study for the following:

- 1. High dose curative radiotherapy within 30 days in the area to be treated.
- 2. Tumor invading a major blood vessel.
- 3. Tumor is not measurable on a CT or MRI scan according to RECIST v1.1.
- 4. Location and extension of the tumor precludes a potentially effective I-PDT.
- 5. Patients with known brain metastases should be excluded from this clinical trial because of their poor prognosis and because they often develop progressive neurologic dysfunction that would confound the evaluation of neurologic and other adverse events.
- 6. Patients with porphyria, or with known hypersensitivity to porphyrins or porphyrin-like compounds.
- 7. Platelet count < 75,000.
- 8. Patients with impaired renal and/or hepatic function (total serum bilirubin > 2 mg/dL, alkaline phosphatase (hepatic), SGOT or SGPT > 3 times the upper normal limit.

- 9. Patients with moderately to severely impaired creatinine clearance (CrCl <44) will be excluded.
- 10. Uncontrolled intercurrent illness including, but not limited to, ongoing or active infection, symptomatic congestive heart failure, unstable angina pectoris, cardiac arrhythmia, or psychiatric illness/social situations that would limit compliance with study requirements.
- 11. Pregnant or nursing female subjects.
- 12. Unwilling or unable to follow protocol requirements.
- 13. Any condition which in the Investigator's opinion deems the subject an unsuitable candidate to receive porfimer sodium.

Refer to Appendix C for the ELIGIBILITY VERIFICATION FORM: EXCLUSION CRITERIA CHECKLIST.

3.3 Special Populations

The following special populations will be excluded from this study:

- Cognitively impaired adults/adults with impaired decision-making capacity
- Individuals who are not yet adults (infants, children, teenagers)
- Pregnant women
- Prisoners

3.4 Inclusion of Women and Minorities

Both men and women and members of all races and ethnic groups are eligible for this study.

4.0 Local and Study-Wide Number of Subjects

In the Phase 1 study, a maximum of 12 (four cohorts of 3) evaluable participants at Roswell Park, will be enrolled. The number of subjects required is a function of the unknown dose-toxicity.

5.0 Local and Study-Wide Recruitment Methods

Participants will be identified/recruited/screened from patients at the Head and Neck Clinic at Roswell Park and participating sites and from multi-disciplinary conference discussion.

6.0 Multi-Site Research

Not applicable-This is a single-site study.

7.0 Study Timelines

A maximum of 12 participants at Roswell Park will be enrolled. Accrual is expected to take 5 years, with follow-up for 24 months from the start of investigational treatment.

8.0 Study Endpoints

8.1 Primary Endpoints

Phase 1:

o The safety will be determined by recording the occurrence of AE during the first 30 days post final I-PDT day, using the revised NCI Common Terminology Criteria for Adverse Events (CTCAE) version 5.0.

Exploratory Endpoint

Objective target tumor response rates will be assessed according to RECIST v1.1 at 12 ± 2 weeks post I-PDT as described in section 16.2.

9.0 Study Design

All participants will meet the inclusion and exclusion criteria summarized in Section 3.1 and Section 3.2 prior to taking part in this study.

This study will recruit subjects with HNC who failed to respond to standard therapy and are not candidates for salvage surgery or radiation therapy including re-irradiation. These HNC subjects would otherwise receive SoC chemotherapy, targeted therapy or potentially immunotherapy as first line palliative care treatment options.

All participants will receive I-PDT. All participants will have a standard diagnostic head and neck scan with CT or MRI, with or without contrast. Participants will be followed according to the 2018-NCCN follow-up guidelines (63; Appendix H) for patients with advanced HNC (https://www.nccn.org/professionals/physician_gls/pdf/head-and-neck.pdf). The study related visits would be up to 2 years, thus every 1-3 months in the first year, and every 2-6 months in the second year. The routine clinical follow up will be up to 5 years. The study schema is shown in

[figure not shown]
[figure not shown]

Figure 3 Study Schema

10.0 Treatment

10.1 The Standard of Care Procedure

All participants will undergo a standard diagnostic head and neck scan with computed tomography (CT) or magnetic resonance imaging (MRI) as clinically indicated.

10.2 Interstitial Photodynamic Therapy (I-PDT)

10.2.1 Porfimer Sodium Administration

Subjects will receive a single intravenous dose of porfimer sodium that will be administered approximately 48 ± 8 hours before the first I-PDT treatment.

Drug administration will take place in a room that has covered windows to protect the subjects from light exposure that can induce phototoxicity (i.e., direct sun light or visible artificial light that is more than 60 W). The Principal Investigator or designee will inject the subjects with porfimer sodium for this study.

A dose of 2 mg/kg of porfimer sodium will be administered by slow intravenous injection into a vein (3-5 minutes). Light-avoidance measures for approximately 30-90 days will be required. The Clinical Research Coordinator and staff nurses will explain the light-avoidance measures to each subject and written instructions will be handed out to the subjects (**Appendix F**). The subject will be cautioned to protect the site of the infusion from excessive direct sunlight and certain bright lights for up to 3 months. The site may be exposed to normal ambient light.

Vital signs will be done immediately after the end of the injection and 15 minutes after.

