10.3 Definition of Dose-Limiting Toxicity

Dose Limiting Toxicities will include:

Any adverse events (AEs) that are \geq grade 4 that are possibly, probably, or definitely related to the I-PDT, by recording the occurrence of AE during the first 30 days post final I-PDT treatment using the revised the National Cancer Institute (NCI) Common Terminology Criteria for Adverse Events version 5.0 (CTCAE v5.0). Dose Limiting Toxicities will be evaluated for 30 days post final I-PDT day.

If participants experience DLTs, further I-PDT sessions will be held until DLT resolution as well as after porfimer sodium clearance.

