10.4 Dose Escalation/Finding Schema

The FDA approved porfimer sodium dose (2 mg/kg) will not change. We will aim to deliver light fluence rate of ≥ 8.6 mW/cm² and fluence of ≥ 45 J/cm² to 100% of the CTV (dose level 1), as much as possible. Dose level -1 will ≥ 5.0 mW/cm² and fluence of ≥ 45 J/cm² to 100% of the CTV.

Table 2. The study plan for finding optimal fluence rate in I-PDT with Photofrin in patients with LAHNC.			
Dose Level Number of patients with DLT at a given dose level		Decision rules	
Dose Level 1 (Starting): The maximum fluence rate, scaled for	0 out of 3	Enter 3 patients at Dose Level 1 : The laser fluence rate and fluence, scaled for human, which induced maximum photoreaction in the animal models	
human, which induced effective	1 out of 3	Enter 3 more patients at this Dose Level .	

photoreaction in the animal models.	≥2	Enter 3 patients at Dose Level -1 : The laser fluence rate and fluence, scaled for human, which induced minimal toxicity in the animal models.
	≤ 1 out of 6	This is generally the recommended Phase II dose rate/dose. At least 6 patients must be entered at the recommended Phase II dose.

In participants where their tumors may require more than one course of I-PDT for complete effective illumination of the CTV, up to three sessions of I-PDT may be performed, at the discretion of the treating physician. The FDA approves to administer up to three courses of PDT with Photofrin® each separated by at least 30 days in the treatment of esophageal and endobronchial cancer (http://www.photofrin.com/wp-content/uploads/2013/02/prescribing-info.pdf.). Therefore, treatment sessions in this study will be conducted at least 30-days apart. The porfimer sodium dose (2 mg/kg) will remain the same.

See Appendix D 1 for the Dose Escalation Schedule of Events. The date of the last I-PDT course will be used to determine the scheduling of the follow up SoC related to this study.

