 - 10. If possible, intraoperative CT (such as O arm) or another radiological imaging (e.g. C-arm) will be used to image the catheters in the tumor.
 - 11. Refer to Section 10.2.1.
 - 12. Medications ongoing within 1 week prior to porfimer sodium injection.
 - 13. AE reporting period will be for 30 days \pm 2 days post first SOC treatment.
 - 14. First SOC treatment day of I-PDT day if no therapeutic SOC treatment is administered.
 - 15. Refer to Section 11.6f patient doesn't come in or quality of life is missed, may be done via telephone.
 - 16. In the event that the tumor size is such that treating the entire tumor could cause a health risk to the patient, the current I-PDT course will be broken up into session/s. We will illuminate one part of the tumor on the day of I-PDT and another part/s of the tumor in additional I-PDT session/s within 14 days after the initial I-PDT session, at the discretion of the treating physician. If

- an I-PDT course is broken up into I-PDT sessions, the I-PDT dosage for each session will remain the same as though sessions were not broken up as dosing is dependent on number of fibers received per session. The patient will not need to receive additional doses of porfimer sodium if having additional I-PDT sessions within 14 days after the previous I-PDT session as porfimer sodium is expected to be in the tumor for at least 30 days.
- 17. Another (one or two, total of three) laser light treatment(s) only (no additional drug) within 2-3 weeks of the initial administration of Photofrin.
- 18. Patient may receive a second complete I-PDT treatment that will include drug and light administration. It will be at the discretion of the treating physician to administer this additional treatment. Another CT (charged to the study if it is not SoC) will be done, and all tests will be conducted before and after additional treatment, according to the same schedule parameters as the initial treatment.

Appendix D 1 Schedule of Procedures and Observations (Only for Dose Escalation later I-PDT Sessions if Deemed Necessary by Physician)**

Evaluation	Repeat of Initial Tests and Procedures ^A	Pre- Operative	Day of Treatment	1-week Post- treatment	Clinic Visit	Post- Treatment	Follow- Up
Physical Exam/ Vital signs ^B & pain assessment using a verbal score 0-10	X			X	X	X	X
Hematology ^C and Chemistry ^D	X			X	X	X	
Research Blood Draws ^E			X	X	X	X	X
Pregnancy Test (Urine)	X						
ECOG Performance Status	X		X	X	X	X	X
UW-QoLQ v. 4 ^p	X			X	X	X	X

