 - F. If required per physician's discretion, standard tumor staging performed within 4 weeks, and at least 14 business days prior to following I-PDT. If possible, the imaging will include temporary fiducial markers that will be affixed to skin. Refer to Section 11.2.
 - G. CT scans at 10 to 12 weeks post I-PDT and as clinically indicated following the NCNN 2018 guidelines.
 - H. If tumor results determine porfimer sodium infusion is needed for later 2nd and 3rd I-PDT sessions, infusion will occur 48 hours ±8 h prior to illumination. Vitals are to be taken immediately after injection and after 15 minutes.
 - I. If possible, intraoperative CT (such as O arm) or another radiological imaging (e.g. C-arm) will be used to image the catheters in the tumor.
 - J. Refer to Section 10.2.1.
 - K. Medications ongoing within 1 week prior to illumination.
 - L. Refer to Section 10.2.1.
 - Li. The later 2nd and 3rd I-PDT study treatments total as per the physician's discretion are at least 30 days apart from each other (see Section 10.4). For additional I-PDT treatments that are 30 days from the previous that require an additional dosage of porfimer sodium the porfimer sodium (2mg/kg) is administered 48 hours prior to illumination.
 - M. AE reporting period will be for 30 days \pm 2 days post first SOC treatment.
 - Oi. Since there may be up to three I-PDT courses, at least 30 days apart (see Section 10.4), per the physician's discretion, adverse events review of previous study treatments are reviewed prior of the next additional I-PDT.
 - N. In Phase 1, patients are off treatment/on follow up as clinically indicated 30 days after the last I-PDT.
 - O. Refer to Section 11.6 if patient doesn't come in or quality of life is missed, may be done via telephone.

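### The protocol does not say consistently whether an I-PDT course given 30 days or more after the last one carries a new porfimer dose

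*Combined protocol and SAP*

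**What the plan says.** The drug instructions are spread over the treatment section and two schedule appendices.

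- Section 10.2.1: "Subjects will receive a single intravenous dose of porfimer sodium that will be administered approximately 48 ± 8 hours before the first I-PDT treatment". Nothing there refers to a later course. Section 11.3 likewise describes one injection.
- Section 10.4, on the design: "The FDA approved porfimer sodium dose (2 mg/kg) will not change". Levels 1 and -1 differ in fluence rate only. On repeat treatment: "up to three sessions of I-PDT may be performed, at the discretion of the treating physician", at least 30 days apart, and "The porfimer sodium dose (2 mg/kg) will remain the same".
- Section 10.3, after a DLT: "further I-PDT sessions will be held until DLT resolution as well as after porfimer sodium clearance".
- Appendix D notes 16 and 17, and Appendix D 1 note P: extra light within 14 days (16 and P), or within 2 to 3 weeks of the injection (17), is given without new drug. Notes 16 and P explain that porfimer is expected to stay in the tumor for 30 days or more.
- Appendix D note 18: "Patient may receive a second complete I-PDT treatment that will include drug and light administration". The porfimer row of that table is marked in the matching column without a condition.
- Appendix D 1 note H sets a condition: "If tumor results determine porfimer sodium infusion is needed for later 2nd and 3rd I-PDT sessions, infusion will occur 48 hours ±8 h prior to" the light. Note Li: "For additional I-PDT treatments that are 30 days from the previous that require an additional dosage of porfimer sodium", 2 mg/kg is given 48 hours beforehand.

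**The concern.** For a course at least 30 days after the previous one, re-dosing is unmentioned in 10.2.1, implied in 10.4, definite in note 18 and conditional in notes H and Li. No passage says which finding meets the condition. Two treating physicians could each follow the text and give different drug exposure before the same illumination.

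This matters because the trial's main output is a recommended irradiance, and the levels that produce it are defined by light alone. Section 10.3 evaluates DLTs until 30 days after the final I-PDT, so all of a patient's courses reduce to one yes or no. Section 19.6 tabulates toxicities by grade, pooled over dose levels and cycles, with no breakdown by porfimer doses received. Light delivered on fresh drug and the same light delivered on residual drug would count as the same exposure. The point concerns which drug dose accompanies a session, not the spacing of sessions.

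**Working it through.** **1. The plan's own figure.** Two light levels × 6 patients = 12, and four cohorts × 3 = 12 (Sections 4.0 and 19.1). This reproduces, and nothing below changes it.

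**2. The passages side by side.**

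| Place | Timing of the later light | New porfimer dose? |
|---|---|---|
| App. D note 16, App. D 1 note P | within 14 days | no |
| App. D note 17 | within 2 to 3 weeks of injection | no |
| 10.2.1 | not addressed | one dose, before the first I-PDT |
| 10.4 | at least 30 days | amount unchanged; repetition not stated |
| App. D note 18 | column headed at least 6 weeks | yes |
| App. D 1 notes H, Li | 2nd and 3rd; at least 30 days | conditional, no criterion |

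The first two rows agree with each other. The disagreement lies in the last four.

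**3. Does residual drug settle the later courses?** The first illumination is 48 ± 8 hours after injection, that is 40/24 = 1.7 to 56/24 = 2.3 days. A second course at the minimum spacing is therefore 30 + 1.7 = 31.7 to 30 + 2.3 = 32.3 days after the first injection, and a third is 61.7 to 62.3 days after it. The documents expect drug in the tumor for 30 days or more and give no upper limit. A light-only course near day 32 is neither clearly covered nor clearly excluded.

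**4. Does the vocabulary separate the cases?** A rule could be built in which a session uses residual drug and a course is re-dosed. The text does not keep to it. Section 10.4 uses both words for the same thing, Appendix D heads its light-only column as a course, and note H calls the conditionally dosed treatments sessions.

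**5. Cumulative drug.** Total = number of doses × 2 mg/kg. With two courses at least 30 days apart, this is 1 × 2 = 2 mg/kg without re-dosing and 2 × 2 = 4 mg/kg with it. With three courses, dosing every one gives 3 × 2 = 6 mg/kg; re-dosing only one later course, which notes H and Li permit, gives 4 mg/kg.

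**6. What it could do to the level decision (illustration).** Table 2 takes both 0/3 and 1/3 to six patients, so a level is accepted if at most 1 of 6 has a DLT. Assume, since the documents give no such figure, an independent DLT risk *p* per course on fresh drug. At the extreme, assume also that a course on residual drug adds no risk. A two-course patient then has risk *p* on residual drug and 1 − (1 − *p*)² on fresh drug.

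- *p* = 0.10: the patient risks are 10.0% and 1 − 0.9² = 19.0%. If all six patients have two courses, the chance that the level passes is 88.6% or 68.0%.
- *p* = 0.05: 96.7% or 89.1%. *p* = 0.20: 65.5% or 30.1%.
- *p* = 0.10 with only one of the six re-dosed: 0.9⁵ × 0.81 + 5 × 0.1 × 0.9⁴ × 0.81 + 0.9⁵ × 0.19 = 0.478 + 0.266 + 0.112 = 85.6%, against 88.6%.

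These are outer bounds. If light on residual drug carries some DLT risk, the gap narrows.

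**The case against.** The best answer is that the passages nearly form a rule. Section 10.2.1 can be read as covering the first course only. Section 10.4 leans on labelled courses of drug and light and most naturally means a repeat dose. Note 18 says so outright, and notes 16, 17 and P explain the early light-only sessions by residual drug. Much of this stands: the early sessions are coherent. What it leaves open is notes H and Li, which make re-dosing conditional at exactly the spacing where this reading needs it to be automatic.

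The objection also disposes of several stronger inferences that a reader might draw:

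- *That the drug dose was promised as fixed per patient.* Section 10.4 fixes the amount per administration, not the number of administrations. Optional courses would vary cumulative drug even under a clear rule.
- *That three courses imply a threefold spread, 2 against 6 mg/kg.* The low end needs light about 62 days or more after the only injection, and no passage prescribes that.
- *That after a DLT a patient would be illuminated with little or no photosensitizer.* This requires a site to apply 10.2.1 to the next session and ignore 10.4 and note 18. A clearance hold more naturally suggests a fresh dose. The actual gap is that 10.3 does not say.
- *That the Appendix D 1 porfimer cell, keyed to J, deliberately points back to 10.2.1.* Notes F to K sit two letters before their table rows: the porfimer text is at H for a cell keyed J, and J's text belongs to the I-PDT row, keyed L. This is a lettering slip.
- *That no assessment could supply a tumor result.* Repeat imaging and a biopsy appear in the schedule. What is missing is the criterion.

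**Conclusion.** The point holds as an internal inconsistency confined to courses at least 30 days after the previous one. For a two-course patient the text supports a total of either 2 or 4 mg/kg. Patients at the same light level may therefore be illuminated on fresh or on residual drug, with nothing in the planned tabulations to tell them apart.

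The number of patients affected cannot be stated, because later courses are optional and the documents do not say how often they are expected. If no one has a later course, the DLT data are untouched. The acceptance probabilities rest on an assumed risk per course, independence between courses and patients, and the extreme assumption of no added risk on residual drug; they show scale only. That one or two patients can tip a level is true of any 3+3 design, but here it means that the recommended irradiance may not be tied to a known drug exposure. The sample size is unaffected. This review takes no position on which dosing rule is right.

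**What to change.** 1. Reconcile Sections 10.2.1, 10.3 and 10.4, Appendix D notes 16 to 18 and Appendix D 1 notes H, Li and P into one statement of which later sessions carry a porfimer dose and on what basis. If dosing is conditional, name the finding that triggers it. Say how the clearance hold in 10.3 relates to dosing at the next session. The choice of rule is for the sponsor and the investigator.
2. Use session and course with one meaning each throughout.
3. Correct the letter shift in the Appendix D 1 footnotes so that the porfimer cell points to the porfimer note.
4. In the safety analysis, list each DLT with the number and dates of porfimer doses and light sessions that the patient received before the event, and report the recommended irradiance with that exposure stated. Porfimer administration is already a scheduled procedure, so the data may already be captured; the case report form is not in the documents and should be checked.

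The cost is amendment wording and one extra listing, with no added patients or procedures.
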